AUTONOMOUS UNIVERSITY “BENITO JUÁREZ” OF OAXACA (UABJO)

STUDY PROTOCOL:

EFFECT OF VITAMIN D SUPPLEMENTATION ON STRENGTH AND MUSCLE GAIN IN OLDER ADULTS WITH OBESITY

NCT: Pending
Document versión: Version 1.0

Principal investigator:
[name]
[contact]
[name]
UABJO

Study Site: Instituto Mexicano del Seguro Social (IMSS)
Family Medicine Unit 24
Miahuatlán de Porfirio Diaz, Oaxaca, Mexico

JUNE 2023

STUDY PROTOCOL

Title: Effect of Vitamin D Supplementation on Muscle Strength and Muscle Mass in Older Adults With Obesity in Miahuatlán de Porfirio Díaz, Mexico (2023–2024)

Principal Investigator: M.N.C. [name] Doctoral Program in Biosciences, Faculty of Medicine, UABJO Email: [contact] [contact]

Study Site: Mexican Social Security Institute (IMSS) Family Medicine Unit No. 24 (UMF 24) Miahuatlán de Porfirio Díaz, Oaxaca, Mexico

Study Design: Randomized, placebo-controlled, parallel-group clinical trial; single-blind (participants).

Study Dates: Start: November 2023 End of follow-up/data lock: April 2024

Background and Rationale: Obesity in older adults is a growing public health concern in Mexico. The coexistence of excess body fat with reduced muscle mass and strength—known as sarcopenic obesity—is associated with frailty, impaired mobility, increased risk of falls, and decreased quality of life. Vitamin D plays an important role in muscle physiology, influencing protein synthesis, mitochondrial function, and neuromuscular coordination. Older adults often have low serum vitamin D levels due to decreased skin synthesis, limited sunlight exposure, and dietary insufficiency. Although randomized trials have evaluated vitamin D supplementation for muscle function, results remain inconsistent, and evidence in Mexican older adults with obesity is limited. This trial evaluates whether high-dose vitamin D improves muscle strength and muscle mass in this population.

Research Question: What is the effect of daily supplementation with 10,000 IU of vitamin D3 for 12 weeks on muscle strength and muscle mass in older adults with obesity receiving care at IMSS UMF No. 24?

Objectives: Primary objective: To evaluate the effect of daily vitamin D3 10,000 IU for 12 weeks on muscle strength and muscle mass in older adults with obesity.

Secondary objectives: 1) To compare changes in body fat percentage, body adiposity index (BAI), abdominal volume index (AVI), and visceral fat. 2) To assess changes in physical performance using the Short Physical Performance Battery (SPPB). 3) To analyze changes in serum 25-hydroxyvitamin D concentrations.

Study Design and Methods: Interventional clinical trial with two parallel arms. Participants are randomly assigned to a vitamin D group or placebo group. The intervention period is 12 weeks per participant.

Study population: Older adults (≥ 60 years) with $\text{BMI} \geq 30 \text{ kg/m}^2$ attending IMSS UMF No. 24.

Inclusion criteria: - Age ≥ 60 years. - $\text{BMI} \geq 30 \text{ kg/m}^2$. - Receiving care at IMSS UMF No. 24. - Ability to perform physical tests (handgrip, SPPB). - Ability and willingness to provide written informed consent. - Willingness to take one capsule daily for 12 weeks and attend all visits.

Exclusion criteria: - Hypercalcemia or major calcium metabolism disorders. - Current use of high-dose vitamin D supplements ($\geq 1,000$ IU/day). - Use of medications affecting vitamin D metabolism (e.g., anticonvulsants, systemic corticosteroids). - Severe renal or liver disease. - Active cancer or recent chemotherapy. - Major musculoskeletal or neurological impairment preventing testing. - Cognitive impairment limiting understanding or cooperation. - Participation in another clinical trial in the last 3 months. - Any condition considered unsafe by investigators.

Intervention: Vitamin D arm: 10,000 IU vitamin D3 (cholecalciferol) oral capsule once daily for 12 weeks. Placebo arm: visually identical placebo capsule once daily for 12 weeks. Participants are asked to maintain their usual diet and medical treatment.

Assessments: Baseline and week 12: - Anthropometry (weight, height, BMI, waist circumference). - Body composition by bioelectrical impedance (muscle mass, fat mass, visceral fat, metabolic age). - Handgrip strength using a handheld dynamometer. - SPPB score. - Serum 25-hydroxyvitamin D.

Sample Size: Planned sample size: 30 participants (approximately 15 per arm), taking into account expected effect size and 80% power. Final analyzed sample: 29 participants.

Statistical Analysis: Normality will be assessed with the Shapiro–Wilk test. Between-group comparisons will be performed with Mann–Whitney U tests for continuous variables, and chi-square or Fisher's exact test for categorical variables. Within-group changes (baseline vs week 12) will be analyzed with Wilcoxon signed-rank tests. A p-value <0.05 will be considered statistically significant.

Ethics: The study follows the Declaration of Helsinki and applicable Mexican health research regulations. All participants provide written informed consent. Data are coded to preserve confidentiality. Risks are considered minimal and include mild discomfort from blood sampling and rare minor side effects of vitamin D. Participants may withdraw at any time without affecting their medical care.

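### The planned between-arm test pools men and women without adjustment and does not say whether it uses week-12 values or change; on week-12 values this costs substantial power

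*Protocol*

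**What the plan says.** - **Allocation** (Protocol, Study Design and Methods): "Participants are randomly assigned to a vitamin D group or placebo group". No blocking or stratification factor is named, and none is ruled out.
- **Size** (Sample Size): "Planned sample size: 30 participants (approximately 15 per arm), taking into account expected effect size and 80% power". The same paragraph adds "Final analyzed sample: 29 participants". No effect size or SD is given.
- **Eligibility** (Inclusion and Exclusion criteria): nothing restricts sex, and the protocol does not mention sex.
- **Main aim** (Objectives section): "To evaluate the effect of daily vitamin D3 10,000 IU for 12 weeks on muscle strength and muscle mass in older adults with obesity". It does not say whether the outcome is the week-12 level or the change.
- **Measurements** (Assessments): handgrip and impedance muscle mass are both taken at baseline and at week 12, so a baseline value is available for adjustment.
- **Analysis** (Statistical Analysis): "Between-group comparisons will be performed with Mann–Whitney U tests for continuous variables". Change is mentioned for the within-group Wilcoxon tests and in the secondary objectives, but not for the between-arm test. The threshold is "A p-value <0.05 will be considered statistically significant", with no sidedness given.

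**The concern.** Handgrip strength and muscle mass vary widely between people, and sex is expected to account for much of that variation (an outside assumption; the protocol gives no figure). A Mann–Whitney test on week-12 values ranks everyone together, so this variation widens the noise against which the treatment effect is judged. With about 15 per arm there is little power to spare. A chance excess of a few men in one arm would also move the observed difference in that particular trial. Both problems can be largely removed with information collected at entry, but the planned test uses none of it.

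**Working it through.** **1. The plan's own figure.** The 30 participants at 80% power cannot be reproduced, because no effect size or SD is stated. Solving backwards, two-sided 0.05, 15 per arm:

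d = (1.960 + 0.842) × √(2/15) = 1.02 SD (normal approximation); 1.05 for Mann–Whitney (efficiency 0.955); 1.06 for a t-test.

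The design is therefore powered only for an effect of about one SD.

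**2. Assumptions (none is in the protocol).** 9 men of 30 (6 to 15 tried); handgrip gap between the sexes 10 kg; within-sex SD 6 kg; effect 6 kg, which is 1.0 within-sex SD and so close to what the design can detect; baseline to week-12 correlation 0.85.

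**3. Chance sex imbalance, 15/15 without stratification.** The number of men in one arm is hypergeometric. With 9 men, the difference is 3 or more unless the split is 4/5 or 5/4:

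P = 1 − 2 × C(9,4) × C(21,11) / C(30,15) = 1 − 2 × 126 × 352,716 / 155,117,520 = 0.43.

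| Men of 30 | 6 | 9 | 12 | 15 |
|---|---|---|---|---|
| P(difference ≥ 3 men) | 0.17 | 0.43 | 0.26 | 0.47 |

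With 6 or 12 men only even differences can occur, so the entry there is P(≥ 4). An excess of 3 men shifts the arm difference by 3/15 × 10 = 2 kg; an excess of 5 by 5/15 × 10 = 3.3 kg.

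**4. Noise in the week-12 mean difference.** Within-sex part: 2 × 36/15 = 4.80. Sex part without stratification: the SD of the difference in proportions is 0.170, so (10 × 0.170)² = 2.89. SD = √7.69 = 2.77 kg (simulated 2.73 to 2.75). With a 5/4 split of the men, the sex part is (10/15)² = 0.44 and SD = √5.24 = 2.29 kg (simulated 2.26 to 2.29).

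**5. Power on week-12 values (simulation, assumptions as in step 2).**

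| Assignment | Pooled Mann–Whitney | Van Elteren by sex |
|---|---|---|
| Not stratified | 51% | about 70% |
| Stratified by sex | 50% | 71% |

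Moving down a column changes almost nothing; moving across gains about 20 points. The test is what matters. The size of the loss depends on the gap: with an effect of 1.1 within-sex SD and 9 men, pooled power is 79% at no gap and 71%, 62%, 52% and 43% at gaps of 1, 1.5, 2 and 2.5 SD, while the sex-stratified test stays at about 77-78% under the same unstratified assignment.

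**6. Type I error on week-12 values.** Pooled test, unstratified assignment, 2 SD gap: 4.5% overall. Among the 11% of draws (9 men) in which the arms differ by 4 or more men it is about 21%, against about 5% for the sex-stratified test. Stratified assignment followed by the pooled test rejects only about 1-2% under no effect.

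**7. Change from baseline.** A constant sex gap cancels. SD of change = 6 × √(2 × (1 − 0.85)) = 3.29 kg. For a 3 kg effect (0.91 SD), power is about 64% pooled and 63-64% sex-stratified. For the 6 kg effect of step 5, the pooled test on change exceeds 99%. Using the baseline value thus matters far more than handling sex alone, and the advantage depends on the assumed correlation.

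**The case against.** The strongest reply is that change is a natural reading. Both outcomes are measured twice, the secondary objectives and the within-group tests speak of changes, and the cover title refers to muscle gain. On that reading the sex gap drops out, and a sex-stratified rank test gains nothing or loses a few points. This stands, and it makes the harm conditional. It does not settle the matter, because neither the primary objective nor the between-arm sentence says which variable is tested.

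A second reply is that a statistical analysis plan, not shown here, may specify adjustment. That is possible. However, the protocol itself names the test, and names it without adjustment, so the point rests on what is written.

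A third is that the sex mix, gap, SD and correlation are all brought in from outside, and that no muscle-mass figures are worked. This also stands; the sizes are illustrations over a range.

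Two stronger readings are tempting and are not supported. A reader might infer that the absence of stratified randomisation is the fault. The protocol is silent on stratification rather than excluding it, and step 5 shows that stratifying the assignment alone leaves power unchanged. A reader might also infer that sex imbalance biases the trial or inflates false positives. Overall type I error stays below 5%; the distortion exists only conditional on an unlucky draw.

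**Conclusion.** The point holds in a conditional form. The protocol fixes an unadjusted, pooled rank test for about 15 per arm and leaves open whether it is applied to levels or changes. If applied to week-12 values, power under the stated assumptions is about 51% rather than about 70%, and an excess of 3 or more men in one arm, with probability 17-47%, moves the handgrip difference by 2 kg or more. If applied to change, the power benefit of handling sex is about nil. Overall validity is not in question. This is a worthwhile, nearly free improvement rather than a fatal defect. Its size rests on an assumed sex mix, sex gap, SD and correlation, none of which the protocol supplies.

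**What to change.** State the variable and the adjustment for the primary between-arm comparison of each outcome. Either:

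1. use the baseline already measured: analysis of covariance of the week-12 value with arm, baseline value and sex as terms, or a comparison of change from baseline; or
2. if a rank test on week-12 values is kept, stratify it by sex (van Elteren).

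Permuted blocks within sex are an optional, low-cost addition for balance. If they are used, the test must also account for sex, because the pooled test on week-12 values then becomes very conservative (step 6). Since the Sample Size paragraph already gives an analysed number of 29, allocation may be past changing. In that case only the analysis part applies, and the choice should be dated and declared as made before or after the arms were compared.

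Cost: a sentence in the protocol and a change of test or model; no extra patients, visits or measurements. Downsides: a sex-stratified rank test on change scores can lose up to a few points of power, and with few men a stratum may end one participant short of balance.

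### Hypercalcemia and severe renal disease are exclusions before 10,000 IU/day, but no listed test would detect either if undiagnosed, or a calcium rise on treatment

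*Protocol*

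**What the plan says.** The Exclusion criteria in the Protocol include "Hypercalcemia or major calcium metabolism disorders" and "Severe renal or liver disease". Neither has a definition, a cut-off or a named test. A further criterion leaves room for judgement: "Any condition considered unsafe by investigators". Under the Inclusion criteria, participants must already be "Receiving care at IMSS UMF No. 24".

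The Intervention section gives the active arm "10,000 IU vitamin D3 (cholecalciferol) oral capsule once daily for 12 weeks". The Background and Rationale calls this a high dose: "This trial evaluates whether high-dose vitamin D improves muscle strength and muscle mass in this population". The Exclusion criteria also bar "Current use of high-dose vitamin D supplements", setting that level at 1,000 IU/day or more.

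The Assessments section names two time points, baseline and week 12. It lists anthropometry, body composition by bioimpedance, handgrip strength, SPPB and one laboratory measurement, "serum 25-hydroxyvitamin D". No separate screening panel and no assessment between the two time points is described. The Ethics section regards the risks as minimal and expects side effects of vitamin D to be rare and minor.

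**The concern.** The plan itself judges that people with hypercalcemia or severe renal disease should not receive the study treatment. Hypercalcemia is defined by a blood value, and severe renal disease is ordinarily identified by one, yet the plan measures neither calcium nor creatinine. As written, the two exclusions can remove only people whose condition is already known.

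Two things follow. A person with undiagnosed disease, whom the protocol means to keep out, could be given the high dose. And a rise in calcium during treatment would go unseen, because no listed test would show it. The protocol also does not describe how adverse events are recorded; that is noted as an omission and nothing is inferred from it.

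This is a matter of participant safety. It does not bear on the validity of the comparison of strength or muscle mass.

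**Working it through.** The plan states no figure on this point that could be reproduced, so the main check sets what must be established beside what is measured. All places are in the Protocol.

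| What has to be known | Where it arises | Listed test that would show it |
|---|---|---|
| Hypercalcemia at entry | Exclusion criteria | None: no calcium test |
| Severe renal disease at entry | Exclusion criteria | None: no creatinine test |
| Calcium rise on treatment | Follows from the dose in Intervention | None: no calcium test at any time point |

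Of the five groups of assessments, four are physical measurements or performance tests. The fifth, 25-hydroxyvitamin D, shows vitamin D status and cannot diagnose hypercalcemia or renal disease. Neither a serum calcium nor a creatinine measurement is named in any other section.

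The arithmetic only describes exposure and cost.

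- **Doses per participant:** one capsule daily for 12 weeks (Intervention) gives 12 × 7 = 84.
- **Cumulative dose:** 84 × 10,000 IU = 840,000 IU per participant in the active arm, which has approximately 15 people (Sample Size).
- **Dose against the protocol's own high-dose level for supplements:** 10,000 / 1,000 = 10. This describes the dose and does not measure hypercalcemia risk.
- **Blood tests listed:** one analyte at two time points; calcium 0, creatinine 0.
- **Assays needed for the fix, 30 participants:** creatinine 30 × 1 = 30; calcium 30 × 2 = 60; total 30 + 60 = 90 at most.

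The number of people who would be wrongly admitted, or whose calcium would rise, cannot be computed. The protocol gives no prevalence of undiagnosed disease and no rate of hypercalcemia at this dose.

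**The case against.** The strongest reply is that this is silence, not contradiction. The protocol is short, and the Assessments section reads as a schedule of outcomes: it contains no screening procedure for any exclusion, including medication use, cognition, cancer or liver disease. Participants are existing patients of the clinic, so records may hold recent results, and investigators may exclude anyone they consider at risk. What remains is undiagnosed disease among about 15 treated people, at an unknown rate.

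Part of this stands. Records and history can find known disease, which is why the point is confined to undiagnosed cases. The gap is of unknown frequency, and the confidence attaches to the absence of a listed test, not to how often harm would follow. The 1,000 IU/day level is a criterion for supplements people already take, not a safety limit, so neither the tenfold ratio nor the 840,000 IU total shows danger.

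The rest does not remove the point. The protocol does not require recent laboratory results or their review. Discretion to exclude supplies no measurement on which to exercise it. A statistical analysis plan does not order blood tests, so its absence from view explains nothing. The renal criterion also names liver disease, for which no test is listed either; leaving that aside here does not weaken the calcium and renal points.

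A fair criticism of the remedy is that a week-12 calcium comes at the end of dosing. It documents a rise present then; it neither prevents one nor shows an earlier rise that has resolved. The baseline check is the protective part.

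**Conclusion.** The concern holds. Followed as written, the plan cannot detect undiagnosed hypercalcemia or undiagnosed severe renal disease before dosing starts, or a rise in calcium at any time up to the end of dosing. The exposure without a listed calcium test is up to 84 doses, or 840,000 IU, for each person in an arm of approximately 15.

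The conclusion assumes that the protocol's list of tests is complete and that no unstated screening results are relied on. No frequency of harm is claimed. This is a change that should be made: it closes a safety gap of unquantified frequency at low cost, and it makes two exclusions already in the plan enforceable for people who do not know they have the condition.

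**What to change.** Add serum calcium and creatinine to the baseline blood sample. Have the investigators write cut-offs for the two exclusions into the protocol, and review both results against them before the first capsule is dispensed. Repeat serum calcium on the week-12 sample in both arms. No cut-off value, dose change or management rule is proposed here; those are clinical decisions.

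The cost is about 30 creatinine and up to 60 calcium assays on blood already drawn, assuming the sample is sufficient, plus one of each for any person excluded on the result and replaced. The protocol does not state the order of blood draw, randomisation and dispensing, so a short delay or an extra contact before dispensing may be needed.

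The Sample Size section already reports a final analysed sample of 29. If dosing is complete, the baseline step can no longer help those participants; the change would then matter for any further use of this plan.

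### The only between-arm test named for muscle strength and muscle mass is an unadjusted Mann–Whitney U, which leaves measured baseline values unused as covariates and usually costs power with about 15 per arm

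*Protocol*

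**What the plan says.** The primary objective (Objectives) is "To evaluate the effect of daily vitamin D3 10,000 IU for 12 weeks on muscle strength and muscle mass in older adults with obesity". The Background and Rationale frames the question as one of improvement: "This trial evaluates whether high-dose vitamin D improves muscle strength and muscle mass in this population".

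Under Assessments, the baseline and week-12 list includes "Handgrip strength using a handheld dynamometer" and muscle mass by bioelectrical impedance. Each primary measure therefore has its own baseline value.

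The Statistical Analysis section fixes the comparison of arms: "Between-group comparisons will be performed with Mann–Whitney U tests for continuous variables". It names no covariate and no adjusted estimate, and it does not say whether week-12 values or changes are compared. The Shapiro–Wilk check has no stated consequence, so Mann–Whitney applies whatever it shows. The only analysis that explicitly uses baseline is within each arm: "Within-group changes (baseline vs week 12) will be analyzed with Wilcoxon signed-rank tests".

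Under Sample Size: "Planned sample size: 30 participants (approximately 15 per arm), taking into account expected effect size and 80% power", and then "Final analyzed sample: 29 participants".

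**The concern.** A Mann–Whitney test on week-12 values ignores baseline. On change, it subtracts baseline in full, however strongly the two measurements correlate. Adjustment by regression uses baseline in proportion to that correlation, so under a linear model with normal errors it is more efficient than either version.

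Two things are at stake. With 29 people power is scarce, and the data that would recover part of it are already collected. Arms this small also often differ at baseline by chance. Comparing week-12 values carries that difference straight into the result, and the Protocol's wording allows that comparison. The named analysis also gives no baseline-adjusted effect estimate.

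This is a point about efficiency and estimation, not validity. Nor does the Protocol say that efficacy will be judged by the within-arm Wilcoxon tests.

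**Working it through.** **The plan's own figure.** No effect size or SD is given, so 30 participants at 80% power cannot be reproduced forwards. Inverted, two-sided 5%, 15 per arm: (1.960 + 0.842) × √(2/15) = 1.02 SD by the normal formula, or 1.06 SD for a t-test. The plan was implicitly sized for a very large effect.

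**Inputs.** From the Protocol: 29 analysed, significance level 0.05. Assumed: a 15 vs 14 split, two-sided testing, the baseline to week-12 correlation r, the effect in SD units, and the data shape.

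**Why adjustment helps (unit SD, normal data).** Per-person variance is 1 for the week-12 value, 2(1 − r) for change, and 1 − r² after ANCOVA.
- ANCOVA relative to week-12: 1 − r² = 0.75, 0.51, 0.19 at r = 0.5, 0.7, 0.9.
- ANCOVA relative to change: (1 − r²)/(2(1 − r)) = (1 + r)/2 = 0.75, 0.85, 0.95.
- Mann–Whitney has a further efficiency factor of 3/π = 0.955 against a t-test.

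**Simulation.** 20,000 trials per setting, with the effect added to the week-12 value of one arm. Mann–Whitney is asymptotic with continuity correction. ANCOVA is least squares with 26 df. Rank ANCOVA is the same model on ranks.

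Power (%), normal data, 0.5 SD effect:

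| r | MW, week-12 | MW, change | ANCOVA | Rank ANCOVA |
|---|---|---|---|---|
| 0.3 | 23 | 18 | 26 | 26 |
| 0.5 | 23 | 23 | 31 | 29 |
| 0.7 | 24 | 36 | 43 | 39 |
| 0.8 | 23 | 50 | 56 | 50 |
| 0.9 | 23 | 80 | 83 | 73 |

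At 1.0 SD, near the implied planning effect, r = 0.5/0.7/0.9: week-12 about 70%; change 70/89/100%; ANCOVA 83/94/100%.

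Effect detectable with 80% power, same r: week-12 about 1.1 SD; change 1.13/0.87/0.50; ANCOVA 0.96/0.79/0.48; rank ANCOVA 1.00/0.84/0.55 SD.

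Power (%), non-normal data, 0.5 SD effect, r = 0.5/0.7/0.9:

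| Shape | MW, week-12 | MW, change | ANCOVA | Rank ANCOVA |
|---|---|---|---|---|
| Lognormal, log SD 0.5 | 34/35/35 | 31/47/89 | 35/48/85 | 44/58/90 |
| Lognormal, log SD 1 | 74/74/74 | 67/84/98 | 54/67/91 | 87/95/100 |
| Bivariate t, 3 df | 40/41/40 | 41/58/94 | 43/56/89 | 50/62/91 |
| Independent t3 errors around a t3 person effect | 35/35/38 | 34/52/92 | 39/52/87 | 44/54/83 |

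Type I error over all shapes: Mann–Whitney 4.2–4.9%, ANCOVA 3.8–5.3%, rank ANCOVA 4.6–5.3%.

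**A second set of runs.** 10,000 trials, 15 per arm, effect scaled so that ANCOVA has about 80% power under normality. Over normal, t5, lognormal (log SD 0.5) and t3 data with r from 0.5 to 0.95, Mann–Whitney had lower power than ANCOVA in all 24 week-12 cells and in 13 of 24 change cells. That is 37 of 48, a few by under 1 point. With t5 data, change fell short of ANCOVA up to r = 0.8 and overtook it at 0.9 (83% vs 80%).

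**Chance imbalance.** The SD of the baseline difference is √(1/15 + 1/14) = 0.372. The probability of a gap above 0.5 SD is 2 × (1 − Φ(0.5/0.372)) = 0.178. In those trials, with no effect and normal data, rejection at r = 0.5/0.7/0.9 is 10/17/22% for week-12 values, 10/8/5% for change and about 5% for ANCOVA.

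**The case against.** The strongest objection is that change is the natural reading: the Protocol speaks of improvement, and its secondary objectives speak of changes. On that reading the advantage of linear ANCOVA is not uniform. Over the five shapes and five values of r in the main runs, it beats Mann–Whitney on change in 12 settings, ties in 1 and loses in 12. At lognormal log SD 1 it loses at every r. Rank ANCOVA does better (19 wins, 2 ties, 4 losses), so one could argue that it should lead. The imbalance figures of 17–22% apply only to week-12 values, and over all randomisations every test stays near 5%. A separate SAP could also add an adjusted analysis.

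Much of this stands as a limit on size. Nearly all the losses come from strong skew or tails as heavy as t with 3 df. ANCOVA wins at every r in normal data and at r up to 0.7 with moderate skew (log SD 0.5). Against week-12 values, which the wording permits, it wins 19 of the 25 settings. Rank ANCOVA is the more robust test, but it falls behind change in normal data at r = 0.9 (73% vs 80%) and does not give a difference in the units of measurement. That is the case for reporting both. As for a SAP, the Protocol itself names the test for all continuous variables, so this is a stated choice and not a detail left open.

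**Conclusion.** The concern holds, as a loss of efficiency and not an error of validity. It should be fixed. If week-12 values are compared, the loss is substantial: in normal data at 0.5 SD, 8, 19 and 60 points of power at r = 0.5, 0.7 and 0.9 (31 − 23, 43 − 24, 83 − 23). If changes are compared, it is modest at 8, 7 and 3 points, and it can vanish or reverse with skewed or heavy-tailed data, mainly at high r. At a 1.0 SD effect and r = 0.5, either Mann–Whitney version gives about 70% and ANCOVA 83%, which straddles the stated 80%.

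Confidence in the size is medium, because r, the effect, the data shape, the 15 vs 14 split and two-sided testing are all assumed.

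**What to change.** For muscle strength and for muscle mass, name one between-arm test of effect: ANCOVA of the week-12 value on arm and the baseline value of the same measure, reported as an adjusted difference with 95% CI. This also settles whether week-12 values or changes are compared, since with baseline in the model both give the same adjusted difference. Name one rank-based version, for example rank ANCOVA, as a sensitivity analysis that is always reported and is not a fallback chosen after looking at the data. For clarity, state that the within-arm Wilcoxon tests are descriptive.

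Because the Sample Size section already reports 29 analysed, label the adjusted analysis post hoc if data have been seen, and report the named Mann–Whitney result beside it.

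The cost is one reworded paragraph and no new data. The real prices are a linear-model assumption, which the fixed rank-based analysis checks, and lower credibility if the post hoc label applies. If change was always intended and r is about 0.9, the gain is only about 3 points in normal data and may be negative otherwise.

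### The between-arm test has no stated quantity or deciding role, while change from baseline is explicitly tied only to within-arm tests at the same 0.05 threshold

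*Protocol*

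**What the plan says.** The trial is randomized and placebo-controlled with two parallel arms (Study Design). The primary objective is "To evaluate the effect of daily vitamin D3 10,000 IU for 12 weeks on muscle strength and muscle mass in older adults with obesity". The first secondary objective is "To compare changes in body fat percentage, body adiposity index (BAI), abdominal volume index (AVI), and visceral fat". The second and third, on the SPPB and on serum 25-hydroxyvitamin D, also speak of change but contain no comparative word.

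For continuous outcomes, the Statistical Analysis section names two tests:

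- "Between-group comparisons will be performed with Mann–Whitney U tests for continuous variables"
- "Within-group changes (baseline vs week 12) will be analyzed with Wilcoxon signed-rank tests"

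One rule covers both: "A p-value <0.05 will be considered statistically significant".

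The first sentence does not give the quantity compared. The second names change from baseline, but separately in each arm. No sentence says which test answers the primary objective, or that the within-arm tests are descriptive.

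**The concern.** A within-arm p-value makes no use of the placebo arm. It mixes any vitamin D effect with whatever else moves both arms: familiarity with the handgrip and SPPB tests at the second visit, season (the study runs from November to April), regression to the mean, and placebo response. A significant result with vitamin D beside a non-significant one with placebo is not a test of the difference between arms. With about 15 per arm, such splits arise easily by chance.

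The objectives are worded largely as changes, and the only analysis sentence that mentions change is the within-arm one. An analyst following the text literally could answer the SPPB and 25-hydroxyvitamin D objectives from within-arm results, and nothing in the protocol would mark that as wrong. A smaller issue concerns power. If the Mann-Whitney test is applied to raw week-12 values, the baseline measurements already planned are not used in the comparison that matters.

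**Working it through.** **Inputs.** From the protocol: 30 participants planned, about 15 per arm; 29 analyzed; significance at 0.05. Assumed: a 15/14 split, two-sided tests, normally distributed changes, and a true change common to both arms, expressed in SDs of change. The protocol gives no value for a common change, so a range is shown.

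**The plan's own figure.** The sample size cannot be reproduced, because no effect size or SD is given. Back-solving for 15 per arm at 80% power gives (1.96 + 0.842) × √(2/15) = 1.02 SD by the normal approximation. This shows the size of effect the trial can detect; it does not check the plan.

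**Step 1: no treatment effect, equal true change in both arms.** 10,000 simulated trials per row; Wilcoxon signed-rank within each arm, Mann-Whitney between arms.

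| Shared change (SD) | Vitamin D arm significant | Placebo arm significant | Vitamin D alone significant | Mann-Whitney on change | Mann-Whitney on week 12 |
|---|---|---|---|---|---|
| 0 | 4.9% | 5.0% | 4.6% | 4.6% | 4.5% |
| 0.25 | 14.2% | 13.3% | 12.5% | 4.6% | 4.6% |
| 0.5 | 42.1% | 40.1% | 24.7% | 4.8% | 4.4% |
| 0.75 | 75.0% | 72.8% | 20.7% | 4.4% | 4.8% |
| 1.0 | 93.5% | 92.3% | 7.3% | 4.7% | 4.5% |

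A separate simulation gives about 14% for vitamin D alone at 0.3 SD and 26% at 0.6 SD.

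**Step 2: check by hand.** The arms are independent, so P(vitamin D alone) = P(vitamin D significant) × [1 − P(placebo significant)].

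- At 0.5 SD: 0.421 × (1 − 0.401) = 0.252, against 0.247 simulated.
- At 1.0 SD: 0.935 × (1 − 0.923) = 0.072, against 0.073 simulated.

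The rate rises and then falls because a large shared change makes both arms significant. The 7% at 1.0 SD therefore applies only to the split-result reading. Someone who looked at the vitamin D arm alone would see significance in 93.5% of such trials.

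**Step 3: what the choice of between-arm quantity costs.** Assume a true effect of 0.7 SD of the week-12 value and a baseline to week-12 correlation of 0.7. The arm-size factor is 1/√(1/15 + 1/14) = 2.69.

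- Week-12 values: 0.7 × 2.69 = 1.88 standard errors.
- Change: SD of change = √(2 × (1 − 0.7)) = 0.775, so 0.7/0.775 × 2.69 = 2.43 standard errors.
- Baseline-adjusted ANCOVA: residual SD = √(1 − 0.7²) = 0.714, so 0.7/0.714 × 2.69 = 2.64 standard errors.

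Simulated power is about 42% for Mann-Whitney on week-12 values and about 71% for ANCOVA. Change beats week-12 values only when 2 × (1 − correlation) < 1, that is, when the correlation exceeds 0.5.

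**The case against.** A reader might infer that the trial tests change only within arms and will therefore credit vitamin D with a change that both arms shared. The text does not support this. A between-arm test is planned and is listed first, and it covers the continuous primary outcomes. Its quantity is unstated, which is not the same as change being excluded. The first secondary objective speaks of comparing changes, most naturally between arms. No sentence makes a split within-arm result the decision rule.

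The between-arm test is also valid on either outcome reading: Step 1 puts its error at 4.4% to 4.8% on change and on week-12 values alike. The inflation therefore depends on a use of the within-arm results that the protocol does not prescribe, and on a shared change whose size it does not give. Nor is the chance that exactly one arm is significant (about 51% at a shared 0.6 SD) a false-claim rate for vitamin D, since roughly half of those trials are significant in the placebo arm only.

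Finally, the quantity compared and the status of the Wilcoxon tests could be settled in a statistical analysis plan that is not shown. That lowers the weight of the point but does not remove it. The protocol does more than stay silent: it fixes inferential within-arm tests of change at 0.05 and does not say that the between-arm test takes precedence.

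**Conclusion.** The point holds as an ambiguity that should be closed, not as an invalid analysis. The protocol leaves open what the Mann-Whitney test compares and whether it decides the objectives, and it explicitly ties change from baseline only to within-arm tests under the same p<0.05 rule.

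The risk is conditional. If split within-arm results were read as a vitamin D effect, the false-claim rate would be about 14% to 26% for shared changes of 0.3 to 0.6 SD, but close to nominal (4% to 5%) with no shared change and about 7% at 1.0 SD. These figures rest on the assumed 15/14 split, normal changes, two-sided tests and the size of the shared change. The correlation does not affect them, because the shared change is expressed in SDs of change.

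The power loss from using raw week-12 values (about 42% against 71%) rests on the assumed 0.7 SD effect and correlation of 0.7. It would be smaller at a lower correlation.

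**What to change.** State in the Statistical Analysis section that efficacy conclusions for every outcome rest on the between-arm comparison, and name it: ANCOVA of the week-12 value adjusted for baseline. If a rank method is preferred, use Mann-Whitney on change from baseline, with a Hodges-Lehmann difference and 95% confidence interval. Report within-arm changes descriptively (median and interquartile range), without p-values.

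The main outcomes are already measured at baseline and week 12, so no new data are needed. The cost is a sentence or two of text and the loss of the within-arm p-values.
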